8.2 Missing Data Conventions

Rules for partial dates are provided in Appendices 2 and 3. These rules will apply to adverse events and medications. Missing values for other variables will not be imputed.

8.3 Data Handling and Transfer

Data will be entered by investigational sites into a clinical database built with DataLabs version 5.0 and exported as SAS® version 9.4 or higher datasets (SAS Institute, Inc., Cary, NC). Converted datasets are created using SAS® and following Clinical Data Interchange Standards Consortium (CDISC) Standard Data Tabulation Model conventions (v3.1.2). Derived analysis datasets are generated using SAS® and following standard CDISC Analysis Dataset Model conventions (implementation guide v1.0). Data analyses including summary tables, figures, and listings (TFLs) are produced using SAS®.

Medical history and AEs will be coded using the Medical Dictionary for Regulatory Activities (MedDRA) version 18.1 to assign a system organ class (SOC) and preferred term (PT) to each AE. AE severity will be graded using Common Terminology Criteria for Adverse Events (CTCAE) version 4.03.

Prior and concomitant medications are coded to preferred drug names using the World Health Organization Drug Dictionary Enhanced (WHODRUG DDE, 2015SEP01).

8.4 Data Screening

The PRA programming of analysis datasets, tables, figures, and listings (TFL) provides additional data screening. Presumed data issues will be output into SAS logs identified by the word “Problem” and extracted from the logs by a SAS macro and sent to Data Management.

Review of a pre-freeze TFL run on clean patients and a post-freeze TFL run on the frozen database allow for further data screening prior to lock. The post-freeze TFLs will be discussed with aTyr in a data review meeting to identify any final data issues and seek corrections prior to database lock. The PRA statistician and aTyr must approve database lock.

8.5 Data Monitoring Board (DMB)

A Data Monitoring Board (DMB), consisting of at least 4 independent physicians and a statistician with expertise in clinical research, clinical immunology, and the clinical management of muscular dystrophies, has been assembled to review safety data and other pertinent data from all ongoing clinical studies of ATYR1940. The ATYR1940 DMB will meet on a quarterly basis to review available, interim clinical safety and other pertinent data as defined for each protocol, from all patients enrolled in studies of ATYR1940, including this study. Data listings will be provided to the DMB approximately every 3 months. The DMB will be managed by aTyr.

9.0 Overall Statistical Considerations

All analyses will use SAS® version 9.4 or higher. Summary tables will be organized overall and by disease group, if applicable, for the two Safety populations. All available data will be used in the analyses, and important data will be included in data listings, sorted by site, patient and by visit within patient.

Unless otherwise noted, categorical data will be presented using counts and percentages, with the number of patients in the corresponding Safety population as the denominator for percentages. Percentages will be rounded to one decimal place except 100% will be displayed without any decimal places and percentages will not be displayed for zero counts. Continuous data, unless otherwise noted, are summarized using the number of observations (n), mean, standard deviation (SD), median, minimum, and maximum. Minimum and maximum will be rounded to the precision of the original value. Mean and median will be rounded to 1 decimal place greater than the precision of the original value. The SD will be rounded to 2 decimal places greater than the precision of the original value, up to a maximum of 3 decimal places. No statistical hypothesis testing will be performed for this study.

9.1 Patient Disposition

The number and percentage of patients enrolled and treated in the study will be presented along with the number and percentage of patients in each analysis population. In addition, the number and percentage of patients who completed and discontinued treatment and the study and the reason for discontinuation will be summarized using the number and percentage of patients.

Patient disposition data will be listed. Inclusion and exclusion criteria will not be listed, but will be contained in datasets.

9.2 Protocol Deviations

Important protocol deviations will be summarized by category using the number and percentage of patients. Categories will include inclusion criteria, exclusion criteria, study drug, safety assessment, visit window, informed consent, prohibited medication, and other (lab/endpoint data, overdose/misuse, etc.).

Important protocol deviations will be listed.

9.3 Demographic and Baseline Characteristics

Demographic and baseline characteristics will be summarized for the following variables:

- Sex (female, male)
- Race (white, black or African American, Asian, American Indian or Alaska native, native Hawaiian or other Pacific Islander, other)
- Ethnicity (Hispanic or Latino, not Hispanic or Latino)
- Age (years)
- Height (cm)
- Weight (kg)
- Body mass index (kg/m^2 : $\text{Weight (kg)}/[\text{Height (m)}]^2$)
- FSHD clinical severity score/LGMD2B disease severity score
- Age at first sign/symptom onset
- Disease duration (years: $[\text{enrollment date of parent study} - \text{date of first sign/symptom onset}]/365.25$; round to one decimal place)
- Years since genetic diagnosis ($[\text{enrollment date of parent study} - \text{date of genetic diagnosis}]/365.25$; round to one decimal place)
- Genetic diagnosis

Demographic and baseline characteristic data, including FSHD clinical severity score, LGMD2B disease severity score, FSHD-related history and LGMD2B-related history will be provided in listings. Data not collected in this extension study will be migrated from the parent study databases.

9.4 Medical History

General medical history ongoing from parent studies will be reported by MedDRA SOC and PT and will be listed.

9.5 Exposure to Treatment and Other Therapies

9.5.1 Extent of ATYR1940 Exposure

ATYR1940 exposure will be summarized using descriptive statistics for overall duration of treatment and for each dose level by 12-week increments. The following variables will be summarized:

- Overall (for both parent studies and the current study)
 - Duration of ATYR1940 treatment (days) = (last infusion date – first ATYR1940 infusion date) + 1
 - Number of doses received
- Dose Level by 12-Week increments (for the current study only)
 - Number and percentage of complete doses given
 - Percent of expected dose received = (actual dose given/planned dose)*100

Exposure data and infusion details will be listed together.

9.5.2 Medications and Therapies

Prior and concomitant medication data will be listed together. Prior and concomitant non-drug therapies and procedures will also be provided in a listing.

9.6 Safety, Tolerability, and Immunogenicity Analyses

9.6.1 Adverse Events, Serious Adverse Events, and Deaths

Adverse events will be collected beginning at informed consent until the end of the study. See Section 6 for definition of TEAE. Adverse events will be coded using MedDRA to assign an SOC and PT to each adverse event and TEAEs will be summarized.

An overall summary of TEAEs including the following categories will be presented for the Safety analysis set by disease group:

- Number of TEAEs reported
- Number and percentage of patients reporting at least one TEAE
- Number and percentage of patients with at least one related TEAE (see definition in Section 6)
- Number and percentage of patients with at least one TEAE leading to study medication withdrawal
- Number and percentage of patients with at least one serious TEAE
- Number of patients with at least one TEAE with fatal outcome

The number and percentage of patients reporting TEAEs will also be summarized for the categories below. Counts will be by patient, not event, and patients will only be counted once within each SOC or PT. Tabulations will be sorted by descending frequency of the number of patients reporting the TEAE for each SOC and by PT within each SOC. Additionally, patients with multiple events within a particular SOC or PT will be counted under the category of their most severe event within an SOC or PT for summaries by maximum grade. Summaries to be provided are the following:

- TEAEs by MedDRA PT
- TEAEs by MedDRA SOC and PT

- Related TEAEs by MedDRA SOC and PT
- TEAEs by MedDRA SOC, PT, and maximum CTCAE grade
- SAEs by MedDRA SOC and PT
- TEAEs leading to study medication withdrawal by MedDRA SOC and PT
- TEAEs with a fatal outcome by MedDRA SOC and PT

TEAEs and non-TEAEs will be listed together.

9.6.2 Laboratory Data

Laboratory data, including hematology, serum chemistry and urine analysis with microscopy, will be collected at Week 1 (if required) and monthly (Week 4, 8, etc) during the Treatment Period, and at 1-Week F/U, 4-Week F/U and 12-Week F/U during the Post-treatment Follow-up period. Additional safety lab assessments will be performed for patients with evidence of generalized IRR. These data will be listed, but not summarized. Table 2 details the parameters assessed.

TABLE 2. LABORATORY PARAMETERS

Hematology	Biochemistry	Urinalysis
Hematocrit	Aspartate aminotransferase (AST)	Color
Hemoglobin	Alanine aminotransferase (ALT)	Specific gravity
Red blood cell (RBC) count	Total bilirubin	Glucose
White blood cell (WBC) count	Insulin-like growth factor 1	Blood
Platelet count	Gamma-glutamyl transferase (GGT)	pH
Neutrophils	Alkaline phosphatase	Protein
Lymphocytes	Blood urea nitrogen	Ketones
Monocytes	Creatinine	Appearance
Eosinophils	Lactate dehydrogenase	Bilirubin
Basophils	Creatine kinase (CK)	Leukocyte esterase (LE)
	CK Isozymes MM	Nitrites
	CK Isozymes MB	Urobilinogen
	CK Isozymes BB	Additional urine microscopic variables ^a
	Troponin I, T	
	Myoglobin	
	Erythrocyte sedimentation rate	
	C-reactive protein	
	Total protein	
	Cholesterol (non-fasting)	
	Sodium	
	Potassium	
	Chloride	
	Bicarbonate	
	Magnesium	
	Calcium	
	Inorganic phosphate	
	IL – 6	
	IL – 1 Beta	

a. Additional urine microscopic variables include: amorphous crystals, bacteria, calcium carbonate crystals, calcium oxalate crystals, calcium phosphate crystals, cysteine crystals, granular casts, hyaline casts, leucine crystals, mucous, RBC, RBC casts, renal epithelial cells, squamous epithelial cells, transitional epithelial cells, triple phosphate crystals, tyrosine crystals, uric acid crystals, waxy casts, WBC, WBC casts, yeast.

Hematology, serum chemistry, and urinalysis will be summarized using descriptive statistics for numeric variables and numbers and percentages for categorical variables at each scheduled assessment. Numeric hematology, chemistry, and urinalysis results will be summarized using CFB as well. Shifts from baseline for clinical laboratory results will be summarized using the number and percentage of patients in each shift category.

Summaries by visit will include data from scheduled assessments, and all data will be reported according to the nominal visit date for which it was recorded.

Laboratory data, including screening serology and pregnancy test results, will be listed. Additionally, sample collection dates and times for HARS, PBMCs, biomarkers, PK, and blood and urine sample for future analysis will not be listed, but will be included in datasets.

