8.5.9. Safety Laboratory Tests

8.5.9.1. Hematology, Serum Chemistries, and Urine Analysis with Microscopy

Blood samples are to be collected for assessment of hematology and serum chemistry parameters and urine samples for urine analysis with microscopy, at the time points indicated in Table 1. Laboratory samples are to be collected after vital signs are measured.

Samples will be analyzed by the central laboratory.

The following safety laboratory parameters will be measured:

Hematology

- Hematocrit
- Hemoglobin
- Red blood cell (RBC) count
- White blood cell (WBC) count
- Platelet count
- Neutrophils
- Lymphocytes
- Monocytes
- Eosinophils
- Basophils

Serum Chemistries

- Aspartate aminotransferase (AST)
- Alanine aminotransferase (ALT)
- Total bilirubin
- Insulin-like growth factor 1
- Gamma-glutamyl transferase
- Alkaline phosphatase
- Blood urea nitrogen
- Creatinine
- Lactate dehydrogenase
- Creatine kinase (CK)*
- Troponin
- Myoglobin
- C-reactive protein
- Total protein
- Cholesterol (non-fasting)
- Sodium
- Potassium
- Chloride
- Bicarbonate
- Magnesium
- Calcium
- Inorganic phosphate

Urine Analysis and Microscopy

- Color
- Specific gravity
- Glucose
- Blood
- pH
- Protein
- Ketones
- Microscopy (including RBCs, WBCs, RBC casts, WBC casts, bacteria, and crystals)

*Elevated CK values will be fractionated.

Safety laboratory tests may be repeated as necessary during treatment at a schedule determined by the Investigator, based on the patient's clinical status.

Abnormal, clinically significant laboratory findings observed are to be reported as AEs, if the finding represents a change from baseline.

Additional safety laboratory tests are required for patients with evidence generalized IRR, as described in Section 8.5.9.4.

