6.0 Definitions

Age

Age will be recorded on the CRF and not derived for this study.

Baseline

Baseline is defined as the baseline in the parent study.

Analyses of changes from pre-infusion to post-infusion (i.e., vital signs, and ECG) will use pre-infusion as well, when applicable. Post baseline values for tabulations will exclude unscheduled visit values; however, unscheduled visit values will be included in listings.

Change from Baseline

Change from baseline (CFB) will be calculated as (post-baseline – baseline). CFB will be calculated for patients with both a baseline and post-baseline value as applicable. Percent CFB will be calculated as (CFB/baseline)*100, where applicable.

If a baseline value has not been recorded for a parameter, then CFB will not be calculated for that parameter. Patients with missing CFB values will be excluded from analyses in which CFB is the endpoint.

Change from pre-infusion

Change from pre-infusion will be calculated as (post-infusion – pre-infusion). Change from pre-infusion will be calculated for patients with both pre-infusion and post-infusion values, as applicable. No imputation will be done for missing values.

Completion of study

A patient will be considered completed in the study when an End of Study CRF page indicates a completion date.

Concomitant medications

Concomitant medications are defined as any medications taken on or after the date of first date of infusion in the parent study. This includes medications that are ongoing at the time of first infusion.

Discontinuation of study

A patient will be considered discontinued from the study when an End of Study CRF page is completed indicating primary reason for discontinuation.

Prior medication

Prior medications are defined as any medications with start and stop dates prior to the date of first date of infusion in the parent study or an ongoing medications with a start date prior to first date of infusion in the parent study.

Protocol deviation

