14.2.2.2.1 Serum Chemistry Results by Visit (Safety Population Cumulative)

Programming Note: Repeat table 14.2.2.1.1. Parameters are listed in Section 9.6.2 of SAP text.

14.2.2.2.2 Shift Summary of Serum Chemistry Results by Reference Range and Visit (Safety Population Cumulative)

Programming Note: Repeat table 14.2.2.1.2. Parameters are listed in Section 9.6.2 of SAP text.

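### CK isozymes appear to be measured only when CK is elevated, yet the SAP tabulates them by visit like any other chemistry test, so their means, changes and shifts describe a selected, changing subset

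*SAP*

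**What the plan says.** Protocol 8.5.9.1 lists creatine kinase among the serum chemistries, with a footnote: "Elevated CK values will be fractionated". The isozymes are not separate items on that list.

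SAP 9.6.2, Table 2, adds them as parameters in their own right ("CK Isozymes MM", followed by MB and BB), with no condition attached. The text below the table says: "Hematology, serum chemistry, and urinalysis will be summarized using descriptive statistics for numeric variables and numbers and percentages for categorical variables at each scheduled assessment". It continues: "Numeric hematology, chemistry, and urinalysis results will be summarized using CFB as well". Shifts from baseline are to be summarised as well.

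The shell for Table 14.2.2.2.1 reads "Programming Note: Repeat table 14.2.2.1.1. Parameters are listed in Section 9.6.2 of SAP text". That gives every Table 2 parameter N, mean, SD, median, minimum and maximum, for actual values and for change from baseline. Table 14.2.2.2.2 does the same for shifts.

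SAP 6.0 sets the rule for change: "CFB will be calculated for patients with both a baseline and post-baseline value as applicable", and "Patients with missing CFB values will be excluded from analyses in which CFB is the endpoint". SAP 8.2 rules out imputation of laboratory values. Nothing exempts the isozymes or marks their rows as conditional on CK.

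**The concern.** Read together, these rules make membership of an isozyme row depend on the quantity being summarised. A patient whose CK returns to normal has no isozyme result at that visit and leaves the row. A patient with normal CK at baseline never enters the change-from-baseline row. The set of contributors therefore changes from visit to visit, and it changes because of the outcome.

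The shift table has the same problem. Its percentages use patients with both a baseline and a post-baseline result, so patients without an isozyme value appear only as missing, with nothing to show that they are missing because CK was normal.

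Protocol 2.3 treats serum CK as circulating evidence of muscle disease, and safety is the first study objective. With up to 24 patients split into three disease groups, an isozyme row could rest on a handful of selected patients and be read as a trend in the whole group.

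**Working it through.** The plan has no figure to reproduce: no hypothesis test, no formal sample size and no stated CK distribution. The check shows the direction and possible size of the selection.

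**Assumptions (none from the documents).** CK is log-normal with log-scale SD s = 0.6. The upper limit is L = 200 U/L. The correlation between baseline and visit is r = 0.8 on the log scale. There is a true proportional fall of 30%. The isozyme is a fixed fraction of CK and is reported in absolute units. Figures below are on the CK scale; a fixed fraction multiplies them all alike.

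**Formulas.** For a median m, let z = ln(L/m)/s.
- Mean over all patients: m·exp(s²/2).
- Mean among those above L: m·exp(s²/2)·Φ(s − z)/Φ(−z).
- For change from baseline, take the means at the two times among those above L at both. With z0 for baseline and z1 for the visit, the share is Φ₂(−z0, −z1; r). The baseline mean is the overall baseline mean times Φ₂(s − z0, rs − z1; r) divided by that share. The visit mean follows by symmetry.

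**Worked case, baseline median 200.**
- The overall mean is 200·exp(0.18) = 239.4, falling to 0.7 × 239.4 = 167.6. The true mean change is -71.8.
- z0 = 0 and z1 = ln(200/140)/0.6 = 0.5945.
- Mean among those elevated at baseline: 239.4 × 0.7257/0.5 = 347.6.
- Mean among those elevated at the visit: 167.6 × 0.5022/0.2761 = 304.9.
- Difference between by-visit means: -42.7, a fall of 12% rather than 30%.
- Share elevated at both times: 0.2529, or 24 × 0.2529 = 6.1 patients. Their means are 414.7 and 310.9, so mean change from baseline is -103.8.

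| Baseline median (U/L) | Elevated at visit | Patients of 24 with a change value | True mean change | Difference of by-visit means | Mean change from baseline, as tabulated |
|---|---|---|---|---|---|
| 200 | 28% | 6.1 | -71.8 | -42.7 | -103.8 |
| 250 | 41% | 9.3 | -89.8 | -58.1 | -119.2 |
| 400 | 71% | 16.7 | -143.7 | -112.4 | -164.8 |
| 1,000 | 98% | 23.5 | -359.2 | -350.3 | -363.3 |
| 2,000 | 99.9% | 24.0 | -718.3 | -717.6 | -718.6 |

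Simulation with 2 million draws agrees (-42 and -103 in the first row). The two columns that the SAP would print err in opposite directions, because the patients kept for the paired change are those with the highest values.

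**A different form of change.** CK in multiples of the upper limit: log-scale SD 0.8, additive change with mean -0.5 and SD 1.0, CK floored at 0.05, isozyme 95% of CK.
- Median 1.5: the true mean change is -0.33. Tabulated change is -0.13, now too small, and the by-visit means differ by +0.17, the wrong sign.
- Median 1.5 with a mean rise of +0.5 instead: tabulated change is +0.62 against a true +0.50.
- Median 10: tabulated change (-0.45) is close to the truth (-0.47). The by-visit difference (-0.25) is still off, because a few patients cross the limit even there.

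The direction therefore depends on how CK changes. The size depends on how many patients cross the limit.

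**The case against.** The strongest reply is that little depends on these rows. The study is descriptive, CK isozymes are not a named endpoint, and no stopping rule uses them. Total CK is in Table 2 for everyone, and its low/normal/high shift table already shows how many patients are elevated. The shell prints N separately for actual values and for change, and every result goes into Listing 16.2.10. All of this stands, and it keeps the point minor. A printed N shows that values are missing, but not that they are missing because CK was normal.

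A second reply is that the illustration is most striking for medians near the limit, whereas Protocol 2.3 speaks of pathologic CK levels. This also stands: at 5 times the assumed limit the 30% fall is recovered almost exactly. If fractions are reported as percentages rather than in absolute units, the numbers above do not apply, although the selection remains.

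Third, the footnote does not contain the word only. Restricting fractionation to elevated values is its natural reading, but it is an inference, and SAP Table 2 is unconditional. CK-MB is also on the protocol's Table 7 biomarker list without a CK condition; those results fall outside this SAP, so they do not repair this table.

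A reader might infer that the tables would always understate a fall in the isozymes. The documents do not support that. The laboratory shell prints absolute change, not percent change, and mean absolute change is overstated in every proportional-fall case near the limit shown above.

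**Conclusion.** The point holds as a minor inconsistency. If fractionation is confined to elevated CK, the SAP's isozyme means, changes and shifts describe a selected subset that changes between visits, and they can be biased in either direction. Under the assumed proportional fall with the median at the limit, one printed column shows about 60% of the true change (42.7/71.8) and the other about 145% (103.8/71.8). A reader could not recover the truth from either.

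The size rests on assumed values for the CK distribution, the upper limit, the correlation and the form of change, and on the parent-study baseline having been fractionated under the same rule, which the documents do not say. It is negligible if nearly all patients stay at 5 or more times the limit.

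It would go too far to infer that CK monitoring is compromised: total CK is measured and summarised in all patients.

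**What to change.** In SAP 9.6.2, state that CK-MM, CK-MB and CK-BB are excluded from the by-visit mean and change-from-baseline table (14.2.2.2.1) and from the shift table (14.2.2.2.2), and are kept in Listing 16.2.10. Use total CK, with its existing shift table, for change over time. Add one row per visit giving the number with elevated CK-MB out of the number fractionated, with a footnote that isozymes are available only when CK is elevated.

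If the isozymes are in fact run on every sample, the tables can stay as they are. Protocol 8.5.9.1 and SAP Table 2 should then be reconciled to say so.

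The cost is one sentence, one count row and its footnote. The loss is that no mean isozyme values are tabulated; no listed data are lost.
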